3.2. Primary and Secondary Measures and Endpoints

3.2.1. Primary Efficacy Variable and Endpoint

The primary endpoint for this study will be brain atrophy (BA) as defined by the percentage in brain volume change (PBVC) from baseline to week 48.

3.2.2. Secondary Efficacy Variable and Endpoint

- Time to confirmed disability progression (CDP), defined as increase in EDSS of ≥ 1 point from baseline EDSS if EDSS at entry is ≤ 5.0 , or increase of ≥ 0.5 point if EDSS at entry is ≥ 5.5 . This increase should be confirmed after at least 12 weeks. Progression cannot be confirmed during a protocol defined relapse, although relapses are rare in PPMS.
- Time to CDP as measured by 2 types of events for each individual (progression cannot be confirmed during a protocol defined relapse):
 - An increase from baseline in EDSS score (≥ 1 point from baseline EDSS if EDSS at entry is ≤ 5.0 , or increase of ≥ 0.5 point if EDSS at entry is ≤ 5.5), confirmed after at least 12 weeks, **or**
 - An increase of at least 20% from baseline in the timed 25-foot walk (T25FW) score, confirmed after at least 12 weeks.
- Change from baseline to week 48 in the timed 25 foot walk (T25FW) score.
- The number of new T2 brain lesions at week 48.

3.2.3. Exploratory Efficacy Variables and Endpoints

- Change from baseline to week 48 in the Brief International Cognitive Assessment for Multiple Sclerosis BICAMS score (CVLT-II, BVMT-R, and SDMT).
- New T1-hypointense lesions, changes in T1-hypointense lesion volume, and changes in T2 lesion volume.
- Other magnetic resonance imaging (MRI) parameters, including thalamic, cortical, white matter, and cervical cord atrophy, number of cervical cord T2 lesions, and normal-appearing brain tissue average magnetization transfer ratio (MTR).
- Time to CDP as measured by at least 1 of 4 types of events for each individual (progression cannot be confirmed during a protocol defined relapse):
 - An increase from baseline in EDSS score (≥ 1 point from baseline EDSS if EDSS at entry is ≤ 5.0 , or increase of ≥ 0.5 point if EDSS at entry is ≥ 5.5), confirmed after at least 12 weeks **or**
 - An increase of at least 20% from baseline in T25FW test, confirmed after at least 12 weeks **or**
 - An increase of at least 30% from baseline in the 9-Hole Peg test (9HPT) score, confirmed after at least 12 weeks **or**

- A decrease of at least 20% from baseline in the symbol digit modalities test (SDMT) score, confirmed after at least 12 weeks
- mRS (at week 72, visit 8)
- Time to CDP confirmed after at least 24 weeks.
- T25FW.
- 9HPT.
- Low contrast visual acuity (LCVA).
- 12-Item Multiple Sclerosis Walking Scale (MSWS-12).
- The primary endpoint of Brain Atrophy as defined by the percentage in brain volume change (PBVC) from baseline to week 48 by gender.
- Secondary endpoint of Time to confirmed disability progression (CDP), defined using EDSS by gender.
- Secondary endpoint of Time to CDP as measured using 2 types of events (EDSS or T25FW) by gender.
- Secondary endpoint of change from baseline to week 48 in the timed 25 foot walk (T25FW) by gender.
- Secondary endpoint of the number of new T2 brain lesions at week 48 by gender.

3.2.4. Other Variables and Endpoints

- Relapses.
- Pharmacokinetic measures (determination of plasma concentration of laquinimod).
- Pharmacogenomic (PGx) measures.
- Potential biomarker measures.
- Ancillary studies measures.

3.2.5. Safety Variables and Endpoints

The safety of laquinimod will be assessed throughout the study by evaluating adverse events, vital signs, electrocardiogram (ECG) findings, clinical laboratory parameters, and concomitant medication usage.

3.2.6. Tolerability Variables and Endpoints

- Proportion of patients (%) who prematurely discontinue treatment, reasons for discontinuation, and time to early termination (ET).
- Proportion of patients (%) who prematurely discontinue treatment due to adverse events, and time to ET due to adverse events.

3.2.7. Pharmacokinetic Variables and Endpoints

Blood samples for determination of plasma concentration of laquinimod will be collected at weeks 4, 8, 12, 24 and 48. The patient should be instructed to take the daily oral dose at the same time each day. The date and time of the blood sample, as well as the date and time of the last study drug dose prior to the sample will be recorded in the source document and on the CRF.

Pharmacokinetics of laquinimod will be evaluated in this study using a population pharmacokinetics (PPK) approach. Details of sample collection and processing are provided in the Laboratory Manual.

3.3. Sample Size and Power Considerations

Sample size calculations were based on the following assumptions:

- 2-sided alpha level of 5%
- treatment difference (delta) of 0.3 in PBVC
- standard deviation of 0.8
- drop-out date of 10%

Under the above assumptions in order to reach power of 80%, 125 patients per arm should be enrolled. Since initially, this study was planned to have 3 treatment arms, the original sample size was 375 patients. Although, the enrollment to 1.5 mg laquinimod arm was stopped as specified in Section 3.1 and included 95 randomized patients, the Sponsor decided to continue enrollment to the laquinimod 0.6 mg and placebo arms until the total sample size reaches the initially planned 375 patients. This will result in 140 patients per arm (lauqinimod 0.6 mg/placebo) which provides 84% power.

3.4. Randomization and Blinding

This is a randomized, double-blind, placebo-controlled study. Patients will be randomly assigned to receive treatment with laquinimod at a dosage of 0.6 or 1.5 mg/day, or placebo in a 1:1:1 ratio. From 01 January 2016, patients were randomly assigned to receive treatment with laquinimod at a dosage of 0.6 mg/day, or placebo in a 1:1 ratio. Patients, investigators, and study site personnel will remain blinded to treatment assignment during the study. Laquinimod and placebo will be packaged and administered in a blinded manner. A capped randomization procedure will be employed to ensure that the proportion of EDSS 6.0 and 6.5 patients will not exceed more than 20% of all enrolled patients.

For more details on randomization and blinding see section 3.3 of the protocol.

3.5. Sequence of Planned Analyses

3.5.1. Interim Analyses

No interim analysis is planned for this study.

3.5.2. Final Analyses and Reporting

All final, planned analyses identified in this SAP for part A and part B of this study will be performed only after the last patient has completed part A or part B of the study respectively. The randomization codes will not be unblinded until this SAP has been approved and database has been locked for part A analysis.

4. POPULATIONS /ANALYSIS SETS

4.1. Intent-to-Treat (ITT) Population

The intent-to-treat (ITT) population will include all randomized patients. In this population, treatment will be assigned based on the treatment to which patients were randomized, regardless of which treatment they actually received.

4.2. Modified ITT1 (mITT1) Population

The modified ITT1 (mITT1) is a subset of the ITT population. It will include all patients in the ITT population with at least 1 post baseline PBVC assessment.

4.3. Modified ITT2 (mITT2) Population

The modified ITT2 (mITT2) is a subset of the ITT population. It will include all patients in the ITT population with at least 1 post baseline efficacy assessment (EDSS, SDMT, CVLT, BVMT, T25FW, 9HPT, LCVA and/or MSWS-12).

4.4. Safety (ST) Population

The safety (ST) population will include all randomized patients who receive at least 1 dose of study drug. In this population, treatment will be assigned based upon the treatment patients actually receive, regardless of the treatment to which they were randomized.

4.5. Per-Protocol Population

The Per-Protocol (PP) population is a subset of the mITT1 population and will consist of all patients with no major protocol violations. Details on the final criteria for exclusion from the PP analysis set will be discussed and documented in statistical data review (SDR) meeting prior to revealing the blind.

5. GENERAL ISSUES FOR DATA ANALYSIS

5.1. General

Due to the decision from 01 January 2016 to discontinue the laquinimod 1.5 mg dose arm, and a low study exposure at this time, the laquinimod 1.5 mg dose arm will be presented descriptively only, and will not be included in any inferential analyses.

In addition, both efficacy and safety analyses will be performed using measurements recorded during the study treatment period (i.e., data captured after treatment discontinuation will be excluded from the analyses). MRI parameters measured up to one month after the last dose of the study drug will be considered under study treatment. For all other parameters, data measured up to seven days after the last dose of the study drug will be considered under study treatment. Data captured after treatment discontinuation will be used to identify AEs which occurred after treatment termination.

Descriptive statistics for continuous variables include number, mean, and standard deviation, standard error, median, minimum, and maximum. Descriptive statistics for categorical variables include patient counts and percentages.

Summaries of abnormal and potentially clinically significant abnormal values will include all post baseline values (including scheduled, unscheduled, and early termination visits).

By-visit summaries will present all scheduled visits, including visits that appear after week 48, due to the variable treatment duration of the patients. For patients who perform an ET visit, this visit will be presented as well.

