#### **1.3.2.1. Clinical Pharmacology Studies**

Laquinimod is considered to have high oral bioavailability with linear, time independent and predictable pharmacokinetics, characterized by high plasma protein binding (>98%), high oral bioavailability (~90%), low oral clearance (~0.09 L/h), low apparent volume of distribution (~10 L), and long half-life (~80 h). Absorption under fasting conditions is rapid and maximal plasma levels attained generally within 1 hour after laquinimod administration. Concomitant administration with a high-fat high-calorie meal results in reduction of the absorption rate reflected by prolongation of the time to maximum plasma drug concentration ( $t_{max}$ ) to approximately 5 hours and reduction of the maximum plasma concentration ( $C_{max}$ ) by 30%. Food

however did not significantly affect the overall extent of absorption area under the concentration by time curve (AUC).

Laquinimod is extensively metabolized, predominantly by CYP3A4. Laquinimod metabolites levels in plasma are very low and parent laquinimod is the main systemically circulating entity. Laquinimod pharmacokinetics are affected by moderate and strong CYP3A4 inhibitors (2.5- and 3.1-fold increase in laquinimod systemic exposure, respectively) and strong CYP3A4 inducers. At doses of 0.6 and 1.2 mg, laquinimod is a weak inhibitor of CYP3A4 and a strong inducer of CYP1A2; therefore, laquinimod may affect the systemic exposure of other drugs metabolized by CYP3A4 and CYP1A2. For additional information on concomitant use of laquinimod with CYP1A2 and CYP3A4 substrates, please refer to the IB.

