### **7.1.2. Recording and Reporting Adverse Events**

For adverse event recording, the study period is defined for each patient as that time period from signature of the informed consent form through the end of the follow-up period. For this study, the follow-up period is defined as 30 days after the last dose of study drug.

All adverse events that occur during the defined study period must be recorded on the source documentation and transcribed onto the CRF, regardless of the severity of the event or judged relationship to the study drug. For serious adverse events, the Serious Adverse Event Form must also be completed and the serious adverse event must be reported immediately (see Section [7.1.5.3.1](#)).

At each contact with the patient, the investigator or designee must query the patient for adverse events by asking an open-ended question such as, "Have you had any unusual symptoms or medical problems since the last visit? If yes, please describe." All reported or observed signs and symptoms will be recorded individually, except when considered manifestations of a medical condition or disease state. A precise diagnosis will be recorded whenever possible. When such a diagnosis is made, all related signs, symptoms, and any test findings will be recorded collectively as a single diagnosis on the CRF and, if it is a serious adverse event, on the Serious Adverse Event Form.

The clinical course of each adverse event will be monitored at suitable intervals until resolved or stabilized or returned to baseline, or until the patient is referred to the care of a health care professional, or until a determination of a cause unrelated to the study drug or study procedure is made.

Placebo-Controlled Study – Multiple Sclerosis  
Clinical Study Protocol with Global Amendment 02 Study TV5600-CNS-20006 (ARPEGGIO)

The onset and end dates, duration (in case of adverse event duration of less than 24 hours), action taken regarding study drug, treatment administered, and outcome for each adverse event must be recorded on the source documentation and transcribed onto the CRF.

The relationship of each adverse event to study drug treatment and study procedures, and the severity and seriousness of each adverse event, as judged by the investigator, must be recorded as described below.

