### **1.2.1. Follow-Up of Liver Enzymes After Stopping-Rules Are Met:**

- A patient who meets the above criteria for discontinuation of the study drug should be invited to the site to return the study drug. ET visit activities should be performed as soon as possible.
- Liver enzymes should be monitored until normalization or stabilization of the abnormality, according to the discretion of the investigator.
- In any case, following ET, the minimal follow-up period will be 30 days and will include measurement of liver enzymes at least QW (may be performed in a local laboratory, with at least 1 test being sent to the central laboratory).
- Every effort should be made to complete the additional tests/ evaluations, as described above.

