8.3. Adverse Events

All adverse events (AEs) will be coded using MedDRA. Summaries will be presented for all adverse events (overall and by severity), adverse events determined by the investigator to be treatment-related (overall and by severity), serious adverse events, adverse events causing discontinuation of the study drug, non-serious adverse events, and adverse events by outcome. The AEs will be presented by system organ class and preferred term. Each summary will include number of patients who experienced at least one AE within each category and corresponding percentage from the ST population, number of adverse events within each category and corresponding event rate. For incidence, patients will be counted only once in each system organ

class category and only once in each preferred term category. For frequency in cases when more than one AE with the same preferred term (PT) started on the same date for the same patient, these will be considered as duplicates and will be counted as one AE for that patient. If onset date of AEs with the same PT is partially unknown, then these AEs will be counted as separate AEs. An event rate will be defined as the total number of AEs divided by total exposure to study drug in patient years. Treatment-related adverse event summaries will include adverse events with missing relationship to study drug.

For the summaries by severity, for incidence patients are counted at the greatest severity, and for frequency when cases with duplicate AEs appear, the greatest severity will be assigned for that AE. Adverse events missing the flag indicating serious will be excluded from the summary of serious adverse events but included in the summary of non serious adverse events. For the summary by outcome, for incidence patients are counted at their worst outcome and for frequency when cases with duplicate AEs appear, the worst outcome will be assigned for that AE.

Treatment emergent AEs only which happened under study treatment will be included for all summaries and are defined as events with onset between (including) the date of first study drug dose , up to seven days after the date of last study drug dose. In addition, a summary of all AEs that happened following seven days after the last dose of the study drug will be presented as well.

All analyses presented in the section will be repeated to include both part A and part B when the study is completed.

All AEs will be presented in patient data listings.

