1. For each patient in the ST population, find maximal post baseline value for ALT. If the same maximal value occurs in two separate visits, then the earlier visit value should be taken into account. Following that find the maximal Bilirubin(Total) value occurring after (or same day) the maximum ALT measurement occurred.
2. The maximal values identified in step 1 then should be divided by the ULN for each test accordingly.
3. Values received in step 2 will be presented in the scatter plot with ALT values on the x-axis and Bilirubin values on the y-axis. Two reference lines indicating extreme limits of 3 X ULN for ALT and 2 X ULN for Bilirubin will be shown as well.

Maximal values of AST, ALT and GGT at any time after randomization in terms of the upper normal range multiples will be provided in a separate table for patients with normal AST, ALT and GGT at baseline using descriptive statistics. The following intervals for maximal values will be used for this table: <= 1xULN, > 1xULN and <= 3xULN, > 3xULN and <= 5xULN, > 5xULN and <= 8xULN, > 8xULN. The denominator for calculating percentages will be the number of patients with post baseline hematology tests.

All analyses presented in the section will be repeated to include both part A and part B when the study is completed.

Listings for clinically significant abnormal laboratory data will be presented.

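### The SAP's seven-day limit on safety data keeps serious adverse events starting on days 8 to 30 after the last dose out of the main AE tables, and its rules conflict on which liver tests count

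*SAP*

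**What the plan says.** **The general rule.** SAP 5.1 states that "both efficacy and safety analyses will be performed using measurements recorded during the study treatment period". It sets the limit at one month after the last dose for MRI, and then: "For all other parameters, data measured up to seven days after the last dose of the study drug will be considered under study treatment". The same section makes one exception: "Data captured after treatment discontinuation will be used to identify AEs which occurred after treatment termination". It also says that summaries of abnormal and potentially clinically significant (PCSA) values take in every value after baseline, from scheduled, unscheduled and early termination visits alike.

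**Adverse events.** SAP 8.3 restricts all AE summaries to events with onset from the first dose "up to seven days after the date of last study drug dose". Later events get one summary (tables 15.91.1 and 15.91.2), by system organ class and preferred term. All AEs, serious AEs and deaths are also listed.

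**Liver outputs.** SAP 8.5 builds the eDISH plot from each patient's highest post-baseline ALT, and then says to "find the maximal Bilirubin(Total) value occurring after (or same day) the maximum ALT measurement occurred". Its table of maximal AST, ALT and GGT covers any time after randomization.

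**The protocol.** On AE recording, section 7.1.2 says: "For this study, the follow-up period is defined as 30 days after the last dose of study drug". Once a liver stopping rule is met, Appendix B 1.2.1 says that "following ET, the minimal follow-up period will be 30 days and will include measurement of liver enzymes at least QW". Section 9.6 limits efficacy analyses to the treatment period. Section 9.8, on safety, sets no window. Section 7.1.1 defines possible drug-induced liver injury with hyperbilirubinemia by AST or ALT of at least 3 times ULN, plus bilirubin of at least 2 times ULN or INR above 1.5.

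**The concern.** A rule written for efficacy has been carried over to safety. For efficacy, excluding off-drug data is a choice about what effect to estimate. For safety, it removes events that the protocol requires sites to collect, at a time when drug is still in the body.

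The matter is sharper in this trial than in most. The 1.5 mg arm, with 95 patients randomized, was discontinued as of 01 January 2016 because of cardiovascular events. Every patient still on that dose then entered the post-treatment period. A serious cardiovascular event starting on day 10 would not be counted in the serious-AE table for that arm.

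Liver enzyme elevation is a recognised effect of the drug, and the protocol requires further liver tests after a stopping rule is met. If the general rule governs, the liver tables and the eDISH plot could omit much of that follow-up.

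**Working it through.** The plan gives no figure to reproduce on this point. The check is a comparison of texts with some supporting arithmetic.

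**1. Where a serious AE with onset on day 15 after the last dose would appear**

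| Output | Included? |
|---|---|
| 15.83 all AEs, 15.84 severity, 15.85 and 15.86 treatment-related, 15.87 serious, 15.90 outcome | No: onset is after day 7 |
| 15.91 AEs after study drug discontinuation | Yes, but by organ class and preferred term only |
| Listings 16.2.7.01 to 16.2.7.03 (all AEs, deaths, serious AEs) | Yes: no seven-day limit is stated |

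No table counts serious AEs that start after day 7.

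**2. Share of the AE follow-up cut from the main tables**

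Days 8 to 30 are 30 − 7 = 23 days, and 23/30 = 77%.

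**3. Drug remaining**

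Protocol 1.3.2.1 gives a "long half-life (~80 h"). It also gives a volume of about 10 L and a clearance of about 0.09 L/h, so ln 2 × 10/0.09 = 77 h, which agrees. The fraction remaining is 0.5^(hours since last dose / half-life).

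- Day 7: 168/80 = 2.1 half-lives, and 0.5^2.1 = 23%. For an assumed half-life of 70 to 90 h the range is 19% to 27%.
- Day 30: 720/80 = 9 half-lives, and 0.5^9 = 0.2%.
- Five half-lives: 5 × 80 h = 400 h = 16.7 days.

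**4. The liver rules side by side**

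- For exclusion: the general rule in SAP 5.1, which names safety analyses, and its seven-day limit for all non-MRI parameters.
- For inclusion: the sentence in SAP 5.1 on abnormal and PCSA values; the eDISH input in SAP 8.5 (highest ALT after baseline); and the maximal-enzyme table in SAP 8.5 (any time after randomization).

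Nothing says which governs. Two programmers could draw different eDISH plots from the same data.

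**5. What the excluding reading would remove**

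Take four weekly tests after early termination (ET).

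- ET on the day of the last dose: tests fall at about days 7, 14, 21 and 28, and 3 of 4 are outside the limit.
- ET one or more days later: the first weekly test falls on day 8 or after, and all 4 are outside.

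The plot takes bilirubin only on or after the day of peak ALT. For a patient stopped for liver injury, that can be this same period.

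**6. ALT alone**

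The eDISH plot uses ALT, while protocol 7.1.1 defines the event by AST or ALT. Table 15.108 reports maximal AST, but not jointly with bilirubin. A patient who meets the definition through AST alone would not show in the quadrant that the plot is meant to expose.

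**The case against.** The case on the other side is substantial, and several parts of it stand.

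**Late AEs are not lost.** SAP 5.1 keeps off-treatment data to identify them, 15.91 tabulates them, and the listings show them by treatment group. Deaths also get narratives. What remains is a gap in summary, not in reporting.

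**Inclusion is by onset date.** A liver event that triggers a stopping rule will usually have begun on drug. It then stays in the serious, severity and outcome tables, at its greatest severity and worst outcome, and protocol 7.1.1 makes the liver injury event reportable as serious. This limits the AE gap to events that begin after day 7.

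**A recording period is not an analysis window.** The 30 days in protocol 7.1.2 govern recording. The SAP therefore does not contradict the protocol on the AE window. It does extend a restriction that protocol 9.6 states only for efficacy, without listing this in section 12.

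**The half-life does not by itself justify 30 days.** Five half-lives end at 16.7 days. The arithmetic speaks against 7. The case for 30 is that the protocol already collects AEs to that day, and uses 30 days after the last dose for its contraception and CYP3A4-inhibitor rules.

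Two stronger readings are tempting and are not supported.

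- A reader might infer that the mandated liver tests are certainly left out of the liver and eDISH outputs. The output-specific wording points to inclusion, and a specific rule would usually override a general one. The documents establish a conflict, not an exclusion.
- A reader might set the 1.5 mg arm's days 8 to 30, at most 95 × 23/365.25 = 6.0 patient-years, against the 35 patient-years of trial exposure in protocol 1.4.1.1.7. The dates differ. The 35 is for 191 patients on 15 November 2015, whereas 286 had been randomized before 01 January 2016. Those 191 alone could have added up to 191 × 47/365.25 = 24.6 patient-years by then. The 6.0 also assumes that all 95 were still on drug when the arm stopped.

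**Conclusion.** The point holds for the AE tables. Serious AEs with onset on days 8 to 30, within 77% of the protocol's post-dose AE follow-up, are absent from the serious, severity, relatedness and outcome summaries. They appear only in 15.91, without those breakdowns, and in listings. About 23% of drug remains when the window closes, given the stated half-life. The number of events affected cannot be estimated from the documents.

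For liver data the defect is an unresolved conflict of rules. If the general rule governs, 3 or 4 of every 4 weekly follow-up tests drop out, depending on when the ET visit falls. If the output-specific wording governs, none do. The use of ALT alone in the eDISH plot is a separate, smaller mismatch with protocol 7.1.1 and does not depend on the window.

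This is a gap worth closing at low cost. It does not make the safety report unsound.

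**What to change.** - **AE tables.** Add AE and serious-AE summaries with onset through last dose + 30 days, and keep the seven-day tables beside them. At the least, produce seriousness, severity and relatedness versions of 15.91.
- **Liver window.** State in SAP 5.1 and 8.5 that the PCSA, maximal-enzyme and eDISH outputs use all post-baseline tests, including the mandated liver follow-up.
- **eDISH.** Plot peak ALT or AST, as a multiple of ULN, against peak total bilirubin.
- **Record.** List in SAP section 12 that the on-treatment restriction was extended to safety, with the reason.

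The cost is SAP wording and further runs on data already collected. The 30-day tables will take in a few events unrelated to drug. Event rates will rise slightly unless the follow-up days are added to the denominator, which SAP 8.3 defines as exposure to study drug.
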